### 7.1. Sample Size Calculation

There is no active de novo patient enrollment in this study and all women in the database who meet the inclusion criteria during the recruitment period will be included in the analysis. Therefore, the focus of the sample size calculation was to determine the precision of the estimated incidence rate ratios (IRR) that can potentially be achieved in the study depending on several different hypothetical scenarios of subject accrual. Depending on drug uptake in the participating countries, speed of accrual, event rates, and actual dropout rates, the precision of the estimated incidence rate ratio may change.

The estimates are based on the expected incidence rate of VTE as the primary endpoint. It is estimated that the incidence rate of VTE in women who are not treated with a SERM or HT is 1.74/1000 patient-years (PY), based on data from the placebo groups in bazedoxifene clinical trials. It is assumed that women treated with raloxifene would have a higher incidence of VTE, of 2.17/1000 PY, based on data from the Phase III pivotal trials of bazedoxifene. The rate of VTE observed in the raloxifene arm of the bazedoxifene pivotal trials is lower than the rate reported in the Multiple Outcomes of Raloxifene Evaluation (MORE) trial [1]. In the MORE trial, the incidence rate of VTE was 3.5/1000 patient-years in women randomized to raloxifene. Therefore, our calculations are likely to be substantially more conservative than estimates based on rates in the literature.

All estimates (Table 3, Table 4) were calculated with two-sided 95% confidence intervals. According to the study plan, there will be a 3-year accrual period and each woman will be followed for up to 5 years from enrollment. Since osteoporosis therapies are chronic therapies, it is likely that women will be exposed to the drugs for more than one year. A conservative annual loss to follow up rate of 15% was used in the estimation. Estimates were based on Wald 95% confidence intervals [2]

**Table 3: 95% Confidence Intervals (CI) for Incidence Rate Ratios (IRR) with different numbers of patients in the BZA arm and the primary comparator arm**

Bazedoxifene (n)	Bisphosphonate (n)	BZA:Bisphosphonate	Underlying Incidence Rate Ratio (IRR)		
			1	1.5	2
			95% CI of observed point estimate of IRR		
2150	8600	1:4	0.6, 1.7	1.0, 2.4	1.3, 3.0
2000	8000	1:4	0.6, 1.8	0.9, 2.4	1.3, 3.1
1750	10,500	1:6	0.6, 1.8	0.9, 2.5	1.3, 3.1
1500	12,000	1:8	0.5, 1.9	0.9, 2.5	1.3, 3.2

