The estimated 95% CI of the incidence rate ratios (IRR) in Table 3 imply that if the underlying (true) IRR comparing BZA users to bisphosphonate users is 2, then the point estimate of IRR in the study will lie between 1.3 and 3.2 indicating (a) that the study will be able to rule out equality of the IRRs (i.e., IRR>1) and (b) that the study would not be able to rule out the possibility that the true IRR could be as high as 3.2 or as low as 1.3.

**Table 4: 95% Confidence Intervals (CI) for Incidence Rate Ratios (IRR) comparing BZA users and Raloxifene users assuming equal number of patients in the two arms**

Bazedoxifene (n)	Raloxifene (n)	BZA:Raloxifene	Incidence Rate Ratio (IRR)		
			1	1.5	2
			95% CI of observed point estimate of IRR		
2150	2150	1:1	0.5, 1.9	0.9, 2.7	1.2, 3.4

The estimated 95% CI of the incidence rate ratio (IRR) in table 4 implies that if the underlying (true) IRR comparing BZA users to raloxifene users is 2, then the point estimate of IRR in the study will lie between 1.2 and 3.4 indicating (a) that the study will be able to rule out equality of the IRRs (i.e., IRR>1) and (b) that the study would not be able to rule out the possibility that the true IRR could be as high as 3.4 or as low as 1.2.

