### **7.3. Interim Analysis**

An interim analysis will be conducted once, after **four** (4) years of study data become available.

This interim analysis will include a calculation of crude event rates for the study outcomes in each exposure group. The observed rates of the primary endpoint will be used to determine if the rates are sufficient to continue the study as planned. Based on the results of this interim analysis, the study may be extended in order to accrue the number of events required to preserve the precision of the incidence rate ratios. There will be no other changes in the study design nor will there be any changes needed to the originally planned analysis as a result of this interim analysis.

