**STATISTICAL ANALYSIS PLAN (SAP)
FOR NON-INTERVENTIONAL STUDIES**

**Non-Interventional Study Protocol
B1781044**

**Cohort Study of Venous Thromboembolism and Other
Clinical Endpoints Among Osteoporotic Women
Prescribed Bazedoxifene, Bisphosphonates or
Raloxifene in Europe**

**Statistical Analysis Plan
(SAP)**

Version: 2.0

Authors: PPD [redacted], Pfizer Inc.
PPD [redacted], Medical Research Department,
Cegecim Strategic Data (CSD).

Date: 27-September-2016

PASS information

Title	Cohort Study of Venous Thromboembolism and Other Clinical Endpoints Among Osteoporotic Women Prescribed Bazedoxifene, Bisphosphonates or Raloxifene in Europe.
Protocol number	B1781044
Version identifier of the SAP	2.0
Date of last version of the SAP	27 September 2016
EU Post Authorisation Study (PAS) register number	ENCEPP/SDPP/5395
Active substance	Bazedoxifene
Medicinal product	CONBRIZA
Product reference	EMA/H/C/000913, EU/1/09/511/001-005
Procedure number	EMA/H/C/000913/ MEA 012
Marketing Authorisation Holder (MAH)	Pfizer Limited
Joint PASS	No
Research question and objectives	This observational cohort study is being conducted to characterize the risk of selected adverse events of interest among a patient population prescribed bazedoxifene, raloxifene, or a bisphosphonate in usual clinical care outside of a randomized clinical trial setting. The main study objective is to estimate and compare the incidence rates of venous thromboembolism and other clinical endpoints among women receiving bazedoxifene and women receiving either a bisphosphonate or

	
raloxifene for treatment of osteoporosis. The main objective of the interim analysis is to determine if, based on the incidence rate of the primary endpoint (venous thromboembolism (VTEs)) and the number of patients accrued in each treatment group, there will be sufficient accrual of data/events to continue the study as planned or if there will be a need to amend the protocol and/or extend the study duration in order to accrue the number of events and patients required to preserve the minimal detectable incidence rate ratios targeted in the protocol.

Countries of study
	
Spain, Italy

Authors
	
PPD [redacted], ScD PPD [redacted] Epidemiology
 
Pfizer Inc [name]
 
Tel: PPD [redacted] Fax: PPD [redacted] Email: PPD [redacted]
 
PPD [redacted], PhD Statistician Medical Research Department, Cegedim Strategic Data (CSD)

TABLE OF CONTENTS

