3 INTERIM ANALYSES AND FINAL REPORT

An interim analysis will be conducted once, after four years of study data become available. This interim analysis will include a calculation of crude event rates for the study outcomes in each exposure group. The observed rates of the primary endpoint will be used to determine if the rates are sufficient to continue the study as planned. Based on the results of this interim analysis, the study may be extended in order to accrue the number of events required to preserve the precision of the incidence rate ratios (as defined in the study protocol section 7.1, Sample size calculation). There will be no other changes in the study design nor will there be any changes needed to the originally planned analysis as a result of this interim analysis.

Final analysis will be conducted within 12 months of the end of the study.

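### Protocol 7.1: the Table 3 and Table 4 limits do not follow from the stated inputs, and a range of point estimates above 1 is misread as a guarantee of excluding an IRR of 1

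*Protocol*

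**What the plan says.** Protocol 7.1 gives these planning inputs: a VTE rate of 1.74 per 1,000 PY without a SERM or hormone therapy, 2.17 per 1,000 PY on raloxifene, and two-sided 95% Wald intervals. On follow-up it says "each woman will be followed for up to 5 years from enrollment", and on dropout "A conservative annual loss to follow up rate of 15% was used in the estimation". It gives neither the mean PY per woman nor the expected number of events.

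The text under Table 3 says that if the true IRR is 2, "then the point estimate of IRR in the study will lie between 1.3 and 3.2". Under Table 4 the corresponding statement is "then the point estimate of IRR in the study will lie between 1.2 and 3.4". From each range it concludes that "the study will be able to rule out equality of the IRRs (i.e., IRR>1").

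Later steps depend on this section:

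- Protocol 7.3 says "the study may be extended in order to accrue the number of events required to preserve the precision of the incidence rate ratios".
- SAP section 3 ties the same decision to the "precision of the incidence rate ratios (as defined in the study protocol section 7.1, Sample size calculation").
- The research-question entry in the SAP's PASS information table describes the interim aim as having the events and patients "required to preserve the minimal detectable incidence rate ratios targeted in the protocol".
- SAP 5.4 relies on 7.1 when it calls a 1:6 sample (1,823 bazedoxifene, 10,938 bisphosphonate) adequate.

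**The concern.** There are two separate problems.

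First, the printed limits look too narrow for a cohort that loses 15% a year over at most five years.

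Second, the text treats the sampling range of the estimate at IRR 2 as if it were the confidence interval the study will report. If the central 95% of estimates lies above 1, it follows only that power exceeds 50%. It does not follow that each estimate in that range has an interval excluding 1.

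This is a post-authorisation VTE safety commitment. A reader who believes a doubling is certain to be detected may take too much reassurance from a null result, above all against raloxifene. In addition, the SAP refers to minimal detectable ratios targeted in the protocol, but 7.1 states no detectable ratio and no power. The two disputed sentences are the nearest it comes, so the interim has no clearly defined target.

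**Working it through.** **Formula.** The Wald interval on the log scale is IRR × exp(±1.96 × SE), where SE = √(1/E1 + 1/E0), E0 = n0 × T × rate, E1 = n1 × T × rate × IRR, and T is the mean PY per woman.

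**T from the stated inputs** (15% annual loss, 5-year cap):

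- Lost at the start of each year: 0.85 + 0.85² + … + 0.85⁵ = 3.15
- Continuous loss: (1 − 0.85⁵)/(−ln 0.85) = 3.42
- Lost at the end of each year: 1 + 0.85 + … + 0.85⁴ = 3.71

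**Reproducing the printed limits**, compared at one decimal:

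| T (PY) | Table 3 limits matched (of 24) | Table 4 limits matched (of 6) |
|---|---|---|
| 3.15 | 2 | 1 |
| 3.42 | 3 | 1 |
| 3.71 | 7 | 2 |
| 4.25 (5 × 0.85, loss taken once) | 22 | 4 |
| 4.35 | 23 | 5 |
| 5.00 (no loss) | 12 | 2 |

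The formula is therefore evidently the one used, and rate × PY is what differs. Because only that product matters, the cause cannot be identified. A single 15% cut fits fairly well. A baseline of 2.17 per 1,000 PY with 3.42 PY also matches 22 of 24 in Table 3, but 3.42 PY matches only 1 of 6 in Table 4.

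**Worked row, 1,750:10,500 at IRR 2 and T = 3.42.** E1 = 1,750 × 3.423 × 0.00174 × 2 = 20.8 and E0 = 10,500 × 3.423 × 0.00174 = 62.5. SE = √(1/20.8 + 1/62.5) = 0.253. The limits are 2 × exp(±0.496) = 1.22 to 3.28, against 1.3 to 3.1 printed.

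**Limits at IRR 2 from the stated inputs:**

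| Row | T = 3.15 | T = 3.42 | T = 3.71 | Printed |
|---|---|---|---|---|
| 2,150:8,600 | 1.22–3.28 | 1.24–3.21 | 1.27–3.15 | 1.3–3.0 |
| 2,000:8,000 | 1.20–3.34 | 1.22–3.27 | 1.25–3.21 | 1.3–3.1 |
| 1,750:10,500 | 1.19–3.35 | 1.22–3.28 | 1.24–3.22 | 1.3–3.1 |
| 1,500:12,000 | 1.17–3.43 | 1.19–3.36 | 1.22–3.29 | 1.3–3.2 |
| 2,150:2,150 (raloxifene) | 1.07–3.74 | 1.10–3.65 | 1.12–3.56 | 1.2–3.4 |

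**The inference, taking the printed limits as they stand.** The observed IRR needed to exclude 1 is exp(1.96 × SE) = √(upper/lower).

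- Table 3: √(3.0/1.3) = 1.52 to √(3.2/1.3) = 1.57
- Table 4: √(3.4/1.2) = 1.68

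Letting SE vary with the observed bazedoxifene count (at 4.35 PY) raises these to 1.58–1.65 and 1.73. An observed 1.3 in Table 3 would have an interval between 0.83–2.04 and 0.86–1.97, depending on the row. An observed 1.2 in Table 4 would have 0.71–2.02. Both estimates lie inside the stated ranges, and both intervals include 1.

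**Chance of excluding 1.** Wald power = Φ(ln IRR/SE − 1.96). The likelihood ratio test (LRT, the test named in SAP 8.2.2) was simulated with Poisson counts (400,000 draws, IRR > 1 direction).

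| Comparison | Wald, 4.35 PY | Wald, stated loss | LRT, 4.35 PY | LRT, stated loss |
|---|---|---|---|---|
| Bisphosphonate, IRR 2 | 84–90% | 71–85% | 76–85% | 62–79% |
| Bisphosphonate, IRR 1.5 | 34–40% | 26–35% | 31–38% | 24–33% |
| Raloxifene, IRR 2 | 72% | 58–65% | 75% | 61–68% |

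**The accrued sample, 1,823:10,938, at IRR 2.** Expected events = (1,823 × 2 + 10,938) × T × 0.00174, which is 80.0, 86.9 and 94.1 at 3.15, 3.42 and 3.71 PY. The limits run from 1.21–3.32 to 1.25–3.19. At 1:6, limits that round to the printed 1.3–3.1 need about 99 events (3.91 PY per woman). The 1.3–3.2 in the text needs about 93 (3.66 PY), reached only near the top of the range.

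**The case against.** The best case for the plan has five parts.

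- **Scope.** Section 7.1 chooses precision over power, calls its accrual scenarios hypothetical, and warns that precision may change with actual dropout. That caveat concerns future data. It does not make the printed limits follow from the loss rate said to have been used, and the text itself goes beyond precision when it claims that equality can be excluded.
- **Reading of the sentence.** Its second clause reads like the interval expected if exactly 2 were observed, and on that reading excluding 1 is correct. But the sentence explicitly describes where the point estimate will fall, and the study is not assured of observing 2.
- **Interim target.** Limits that are too narrow make the precision target stricter, and printed limits imply an event count whatever PY was assumed. This stands. It is why recomputing the tables must not be allowed to relax the target. It does not settle which row or limits are meant.
- **Ranges.** The 3.15 PY case is extreme, because 15% of women then contribute no time. Using 3.42–3.71 PY only, Wald power at IRR 2 is 75–85% for Table 3 and 62–65% for Table 4. The Wald figures also fix SE at expected counts, so part of the Wald–LRT gap reflects comparing a formula with a simulation. Both points move the edges of the ranges and leave the conclusion intact.
- **Materiality.** The accrued bazedoxifene group exceeds the 1,750 in the 1:6 row, and the shift in limits is small, so SAP 5.4 is not shown to be materially wrong. That is fair: what is shown is that its benchmark is not met on the stated inputs.

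**Conclusion.** Both parts of the concern hold. The limits in Tables 3 and 4 require about 4.35 PY per woman at the stated rates (4.25 fits nearly as well), against 3.15–3.71 from the stated loss and follow-up. Separately, the claim that equality will be ruled out at IRR 2 fails even on the printed limits. On the stated inputs the chance of missing a true doubling is roughly 15–29% against bisphosphonate and 35–42% against raloxifene by the Wald formula, or 21–38% and 32–39% by simulated LRT.

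The overstatement is moderate. No recomputed IRR-2 interval reaches 1, and no endpoint or analysis is invalidated. The figures assume the protocol's VTE rates, equal mean PY in both groups and unadjusted Poisson counts. Power under the SAP's adjusted Cox model may differ, so these are approximations. Why the tables differ from their inputs cannot be determined from the documents.

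**What to change.** 1. Recompute Tables 3 and 4 from the stated rates, 5-year cap and 15% annual loss, or state the loss, rate and mean PY per woman actually used. Give the expected events per group in either case.
2. Replace both sentences about ruling out equality with the approximate power at IRR 1.5 and 2 for each comparison, under one named test. The LRT would agree with SAP 8.2.2.
3. State in Protocol 7.3 and SAP section 3 which 7.1 row and limits the interim precision target refers to, and bring the minimal-detectable wording in the SAP's PASS information table into line. Recomputed, wider limits should not be used to loosen the target.

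The cost is a set of recomputed planning figures, two reworded sentences and a clarification of the interim target. The sample, endpoints and analysis do not change.

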## 7.2. Safety Analysis

Descriptive statistics on available patient characteristics (e.g., age, BMI, smoking and alcohol use, history of relevant medical diagnoses, use of relevant concomitant medications) will be reported for all exposure groups at baseline.

Incident cases of study endpoints will be included in the analysis. Women with a history of study outcomes recorded in the medical records prior to the index prescription will not be included in the primary analysis for that specific outcome, but will be analyzed separately. For example, a woman with a history of VTE prior to the index prescription will be categorized as a prevalent case and will be excluded from the primary VTE analysis. A

separate analysis for women with a medical history of VTE will be performed and the woman would remain eligible for the analysis of other outcomes as normal. Depending on the number of patients in these subgroups of prevalent cases of each endpoint, this supplemental analysis is likely to have low power to perform any statistical comparison and will be descriptive in nature.

Incidence rates will be calculated for all endpoints in all treatment groups; incidence rate ratios and 95% confidence intervals will be calculated and compared. Stratifications by risk factors of interest (e.g., age, BMI, history of selected medical comorbidities, selected concomitant medications) will be performed for each outcome depending on availability of the data. A multiple regression model may be fit for the primary objective of the study depending on the completeness of the data on potential confounders and accrual of a sufficient number of endpoints.

A time to event analysis may be conducted as a secondary analysis.

All analyses will be conducted for each country separately, as well as after pooling the data from all participating countries.

Given the rarity of certain malignancies in this population, the incidence rates observed in this study may be small and imprecise. In such case, to better characterize the rates obtained in this study, an additional analysis using external reference data for the malignancies may be conducted. The observed frequency of malignancies in all three treatment groups will be compared with the expected frequency calculated from an age and gender matched population-based reference group (e.g., GloboCan) This ratio of observed versus expected events and 95% confidence interval, will be reported.

### **7.3. Interim Analysis**

An interim analysis will be conducted once, after **four** (4) years of study data become available.

This interim analysis will include a calculation of crude event rates for the study outcomes in each exposure group. The observed rates of the primary endpoint will be used to determine if the rates are sufficient to continue the study as planned. Based on the results of this interim analysis, the study may be extended in order to accrue the number of events required to preserve the precision of the incidence rate ratios. There will be no other changes in the study design nor will there be any changes needed to the originally planned analysis as a result of this interim analysis.

## **8. DATA COLLECTION AND DATA MANAGEMENT**

### **8.1. Case Report Forms/Electronic Data Record**

There is no data collection form designed for this study. The data to be used in this study are being collected in an existing electronic health care database.

## **8.2. Record Retention**

To enable evaluations and/or audits from regulatory authorities or Pfizer, the investigator agrees to keep records, including serious adverse event forms, and adequate documentation of relevant correspondence (e.g., letters, meeting minutes, telephone calls reports). The records should be retained by the investigator according to local regulations, or as specified in the Clinical Study Agreement, whichever is longer.

If the investigator becomes unable for any reason to continue to retain study records for the required period (e.g., retirement, relocation), Pfizer should be prospectively notified. The study records must be transferred to a designee acceptable to Pfizer, such as another investigator, another institution, or to an independent third party arranged by Pfizer. The investigator must obtain Pfizer's written permission before disposing of any records, even if retention requirements have been met.

## **9. ADVERSE EVENT REPORTING AND SERIOUS ADVERSE EVENT REPORTING**

This study uses de-identified patient-level electronic health related databases (e-HRD), in which it is generally not possible to link (i.e. identify a potential association between) a particular product and medical event for any individual. Furthermore, while the identifiable patient criterion may be met, the identifiable reporter criterion will not. Thus, the minimum criteria for reporting an adverse event (i.e., identifiable patient, identifiable reporter, a suspect product, and event) are not available and adverse events are not reportable as individual AE reports.

However, this study protocol requires review of the patient medical chart and/or a narrative field in the dataset. If the reviewer identifies a SAE with explicit attribution to any Pfizer drug via patient chart and/or narrative review (and with an identifiable reporter), these SAEs should be reported to Pfizer or its representative for submission to regulatory authorities.

A serious adverse event (SAE) is defined as any untoward medical occurrence that at any dose:

- results in death;
- is life-threatening (i.e., at immediate risk of death due to the event);
- requires inpatient hospitalization or prolongation of existing hospitalization;
- results in persistent or significant disability/incapacity; or
- is a congenital anomaly/birth defect.

Medical and scientific judgment is exercised in determining whether an event is an important medical event. An important medical event may not be immediately life-threatening and/or result in death or hospitalization. However, if it is determined that the event may jeopardize

the patient or may require intervention to present one of the other outcomes listed in the definition above, the important medical event should be reported as serious.

Examples of such events are intensive treatment in an emergency room or at home for allergic bronchospasm, blood dyscrasias or convulsions that do not result in hospitalization, or development of drug dependency or drug abuse.

If there is a written notation in the medical chart/narrative field indicating that a physician attributed a serious adverse event to a Pfizer drug, Pfizer or its representative will complete an SAE form within 24 hours and submit it to Pfizer Safety. Such information will not include any patient or physician identifying information such as name, address, or phone number.

## 10. POTENTIAL WEAKNESSES

**Lack of hospitalization data:** The Cegedim LPD collects data from GP offices. Therefore, complete records of events requiring hospitalization are not available in the database. Since no patient identifiers are available it is also not possible to link to any available national or regional registries to obtain additional information (e.g., vital status, diagnosis of malignancies).

**Data collection in routine care:** The Cegedim LPD collects real life clinical practice information from the actual medical records of the patients. No study specific CRF will be used to collect supplemental information that are not entered in the medical records as part of the patient's routine clinical care. Also, as a non-interventional study, this protocol does not mandate any study specific visits, procedures or laboratory tests.

**Dependence on market uptake of the study medication:** Bazedoxifene is a newly launched product in the participating countries. Since there is no active enrollment of patients (i.e., in contrast to a de novo prospective follow up study), the final sample size will be based on the rate of the uptake of the drug in the participating countries during the subject accrual period.

**Potential for missing data:** The data for this study will come from routine clinical care. No individual patient identifiers will be available. Therefore it is not possible to query the physicians providing the data for any missing information.

**Difference in indication for Bazedoxifene and Raloxifene:** Bazedoxifene is indicated for the treatment of post-menopausal osteoporosis whereas Raloxifene is indicated for both the prevention and treatment of post-menopausal osteoporosis. As a result the characteristics of the cohort of women receiving Raloxifene may differ from the women who are receiving Bazedoxifene. It is possible that the Raloxifene cohort will have a higher proportion of healthier, younger women.

